4.3.1 Baseline Characteristics

Information on the total number of participants per intervention group for each of the following categories will be presented: screened households, screen failures (together with reasons for screen failure), consented participants for the baseline survey, the vaccination and the follow up survey, screen failures (with reasons for screen failure) for baseline and post vaccination surveys and reasons for NP not performed.

Information on the total population and population aged 1 to 9 years from the census, as well as breakdown by sex and distance to nearest health facility will be also summarized by cluster.

Number of vaccinees, by sex and age group will be summarized by intervention group. Participant demographics and data collected through questionnaire at baseline and during post vaccination survey (as describe in section 3.2.3) for each group will be given at individual levels using count and percentages for qualitative variables,

mean and standard deviation (SD) for quantitative variables, and at cluster level using means and standard deviation (or median and IQR if appropriate).

Baseline prevalence of carriage (VT and non VT serotypes) will be measured as the proportion of participants that are respectively colonized with any of the 10 serotypes covered by PCV10 and colonized with any other serotypes, excluding non-typable SP and those confirmed as not colonized by SP.

Proportions will be compared using chi square or Fisher's exact test, as appropriate and adjusting for the clustering effect.

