6.1 Definition of outcomes

Effect of PCV10 campaign

The effect of a single dose PCV10 campaign in the reduction of VT carriage will be assessed by: first, assessing the superiority of a campaign using full doses of PCV10 compared to control group without vaccination; and second, by establishing the non-inferiority of a campaign using fractional doses of PCV10 compared to a campaign using full doses.

NP carriage will be measured in the 3 study arms (full dose arm, fractional dose arm and control arm) in a baseline survey implemented prior to the vaccination campaign and in a post-vaccination survey conducted 6 months post-vaccination campaign.

The NP carriage of VT *S. pneumoniae* will be measured as the proportion of participants that are colonized with any of the 10 serotypes covered by PCV10 at each time point. The reduction in NP carriage will be calculated by comparing the proportion of children carrying VT pneumococci 6 months post-vaccination to baseline, at the time of vaccination. Prevalence of colonization of non-VT serotypes will also be described at both timepoints.

Vaccine safety

Vaccine safety will be monitored up to 28 days after vaccination and all AEs and SAEs will be recorded.

Cost-effectiveness and modelling study

An age-structured, dynamic, deterministic model of pneumococcal transmission will be constructed to estimate the impact of mass fractional dose PCV campaigns on VT carriage. The model will use the

data on social interactions between age groups and PCV coverage estimates collected during the baseline survey as well as the results of the VT carriage from the baseline survey.

Based on the modelled epidemiological impact of PCV10 mass campaigns, with both full and fractional doses, a cost-effectiveness analysis will be performed to estimate the incremental cost-effectiveness ratio of routine PCV10 mass campaigns.

The modelled epidemiological impact and cost-effectiveness of a fractional dose mass campaign will be used to inform ongoing discussions of dose-sparing strategies and the use of single-dose fractional PCV in acute humanitarian emergencies.

Facilitators and barriers to implementing mass campaigns of fractional dose PCV

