Given the sample size of the full-dose arm to test non-inferiority as described above, to test the superiority of a mass campaign to the control (non-vaccinated) arm, and considering a 5% level of significance for a two-sided test and 90%, we would need to sample 9 clusters with 30 households apiece in both the full-dose and control arms. Since the non-inferiority evaluation requires a larger sample size, the control arm will include the larger number of participants per cluster, which will lead to >90% power to detect superiority.

For the NP carriage survey, one participant will be sampled from each household. We consider that most households will have a child aged 1 to 9 years of age, but account for 20% refusal to participate and/or absences and increase the number of households to be invited to participate by 20%. All selected households having a child of the target age group will be invited to participate in the social contacts survey. Table 1 summarizes the number of cluster and households to be included in each survey.

Table 1. Initial estimates of clusters and households to be invited to participate in each survey

Allocation	Nº clusters	Nº households	Total participants
Control arm	9	36	324
Full dose arm	27	36	972
Fractional dose arm	27	36	972
Total	63	108	2268

The baseline prevalence of VT carriage is expected to be between 25 and 35% as described below. In case the results from the baseline survey differ significantly, the sample size may be re-evaluated. Once baseline survey results are available, they will be presented to TSC with simulation on power calculations outlining various

scenarios for the follow-up survey. Sample size may be re-estimated and the number of children may be increased following this review.

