3.2 Assessment of Objectives

3.2.1 Efficacy Assessments

3.2.1.1 Primary outcome

The primary outcome is the prevalence of vaccine-type NP carriage in children approximately 1 to 9 years of age. It will be assessed before vaccination campaign (baseline survey) and at 6 months post PCV10 vaccination campaign (post vaccination survey). VT pneumococci are defined as those covered by PCV10 (1, 5, 6A, 6B, 7F, 9V, 14, 19A, 19F, 23F).

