3.2.1.2 Secondary outcomes

The secondary outcome is the prevalence of non-VT serotypes carriage in children approximately 1 to 9 years of age. It will be assessed as the same timepoints than for the primary outcome, ie during both surveys.

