4.3.2 Primary Analysis

4.3.2.1 Primary Analysis

The primary analysis is the test of the superiority of the full dose vaccination arm compared to the control arm, on the reduction in NP carriage. The reduction will be calculated by comparing the proportion of children carrying VT pneumococci 6 months post-vaccination to baseline, at the time of vaccination.

This primary analysis on the primary endpoint will be performed on the intent to treat population, using generalised estimating equations (GEE) to estimate risk differences and their associated 95% CI for the effect of the full dose vaccination on the reduction in VT carriage compared to the fractional dose. GEE will be used to account for clustering effect. Adjusted analyses with covariates (including but not limited to age, sex, vaccination coverage, time between baseline survey and vaccination, time between vaccination and follow-up survey, baseline prevalence of VT carriage) and stratification factor will be performed.

The administrative vaccination coverage for each site where vaccination campaign is performed, is obtained by the formula:

(number of vaccinees/number of expected children from the age group 1-9 years old) x 100.

The superiority will be tested at the 0.05 significance level.

For the non-inferiority analysis, the 95%CI around the risk difference in the proportion of children with VT carriage (full dose group – fractional dose group) will be using generalised estimating equations (GEE) and non-inferiority will be achieved if the lower limit of this 95%CI is >-7.5%.

Non inferiority analyses will be repeated on the per protocol population. Sensitivity analyses on the primary endpoint will be repeated by analyzing clusters according to the intervention they actually received if misallocation occurred.

In order to account for any potential seasonal variation seen due to timing of the surveys, additional sensitivity analyses will be performed, comparing the difference in prevalence between the full-dose and control arms, relatively to the reduction observed in the control group..

Multivariable logistic regression analyses will be performed to obtain adjusted estimates of risk factors for VT carriage at baseline and after vaccination campaign. The Odds Ratio and 95% CI will be adjusted for age and sex. Robust SE will be used to allow for clustering at the cluster level. 4.3.2.2 Secondary Analysis.

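### The SAP's baseline prevalence sentence can be read as dropping non-colonised children from the denominator, contrary to the protocol; the denominator should be stated for both surveys

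*Combined protocol and SAP*

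**What the plan says.** SAP 4.3.1 (Baseline Characteristics) says that baseline VT and non-VT carriage will be "measured as the proportion of participants that are respectively colonized with any of the 10 serotypes covered by PCV10" and, for non-VT, with any other serotype. It then adds "excluding non-typable SP and those confirmed as not colonized by SP".

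The other places that define or use the same quantity carry no such exclusion:

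- Protocol 6.1: VT carriage is "measured as the proportion of participants that are colonized with any of the 10 serotypes covered by PCV10 at each time point".
- SAP 3.1.5: the primary-outcome data are those of selected children who have a swab result. Negative results are not removed.
- SAP 3.2.1.1: "The primary outcome is the prevalence of vaccine-type NP carriage in children approximately 1 to 9 years of age".
- SAP 4.3.2.1: "The reduction will be calculated by comparing the proportion of children carrying VT pneumococci 6 months post-vaccination to baseline". The non-inferiority comparison in the same section also uses the proportion of children with VT carriage.

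The SAP's secondary outcome (3.2.1.2) is non-VT carriage: "The secondary outcome is the prevalence of non-VT serotypes carriage in children approximately 1 to 9 years of age".

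SAP 1.1 undertakes to explain any change from the protocol's statistical methods. No explanation accompanies the exclusion in 4.3.1.

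**The concern.** The clause names two groups. The second, children confirmed as not colonised, cannot be in any numerator of colonised children. Excluding them therefore either has no effect or takes them out of the denominator. A programmer who assumes that every word is there for a reason could choose the second, and the reported figure would then be the VT share among children with a typable pneumococcus. A third reading is also possible: that the words refer to culture positives not upheld by the PCR check on 10% of positive samples (Protocol 7.5.3). The SAP does not say which is meant.

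Baseline VT prevalence has several uses:

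- the sample-size review (Protocol 7.12, SAP 3.1.2);
- the decision whether to stratify randomisation by baseline prevalence (Protocol 7.11, SAP 3.1.3);
- a listed adjustment covariate (SAP 4.3.2.1);
- the reduction from baseline in each arm (SAP 4.1, 4.3.2.1);
- the seasonal sensitivity analysis, which is scaled to the control-arm reduction (SAP 4.3.2.1).

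The first two are settled before the follow-up survey and cannot be undone at analysis.

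A smaller gap holds on any reading. Non-typable pneumococci are left out, but the SAP does not say whether those children count as non-carriers, form a third category or leave the analysis.

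**Working it through.** **Inputs from the documents.** Planning VT prevalence 30% (range 25-35%); 15% after full dose; ICC 0.02; margin 7.5 points; one-sided 2.5%; 27 clusters of 36 children per vaccine arm; 9 control clusters (Protocol 7.12, SAP 3.1.2).

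**Assumption.** Overall carriage C is not given for this setting. Protocol section 4 cites more than 70% in under-fives in three other countries before PCV introduction. I take C = 70% with a range of 60-80%, and show 50% and 90% as well.

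**1. The plan's own figure, with all sampled children in the denominator.**
- Design effect = 1 + (36 − 1) × 0.02 = 1.70; effective n = 972/1.70 = 571.8 per arm.
- SE = √(2 × 0.15 × 0.85/571.8) = 0.0211.
- Power = Φ(0.075/0.0211 − 1.96) = 94.4%. At 30 children per cluster it is 92.0%.

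Both agree with the stated minimum of 90%. The design figures therefore use all sampled children, as Protocol 6.1 does.

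**2. Reported baseline value if non-colonised children leave the denominator.** Reported share = true VT prevalence / C.

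| C (assumed) | true 25% | true 30% | true 35% |
|---|---|---|---|
| 50% | 50.0% | 60.0% | 70.0% |
| 60% | 41.7% | 50.0% | 58.3% |
| 70% | 35.7% | 42.9% | 50.0% |
| 80% | 31.3% | 37.5% | 43.8% |
| 90% | 27.8% | 33.3% | 38.9% |

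A true 30% leaves the 25-35% band only if C is below 0.30/0.35 = 85.7%. Conversely, at C = 70% a reported 25-35% would mean a true 17.5-24.5% (0.25 × 0.70 to 0.35 × 0.70), so the review could be falsely reassured. These figures ignore the further removal of children with only non-typable isolates, for which no figure is given. At a given C, that removal would push the reported share higher.

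**3. Effect on stratification.** The share depends on overall carriage as well as VT carriage. Two clusters with the same true 30% but overall carriage of 60% and 80% would be reported as 50% and 37.5%, an apparent imbalance in VT carriage that does not exist.

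**4. Carriers-only at baseline, all children at follow-up (C = 70%, no true change in controls).**
- Control: 42.9 − 30 = 12.9-point fall, all spurious (7.5 points at C = 80%, 20 at C = 60%).
- Full dose: 42.9 − 15 = 27.9-point fall against a true 15.
- Difference between arms: 27.9 − 12.9 = 15.0, the true value.

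The shift cancels between arms when baseline VT and overall carriage are balanced. The within-arm reductions do not recover. The seasonal analysis would be scaled to a control-arm fall of 12.9 points instead of zero.

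**5. Carriers-only at both surveys (C = 70%), for completeness.**
- Non-VT fully replaces VT: full dose 15/70 = 21.4%, a fall of 21.4 points; the 7.5-point margin would keep 1 − 7.5/21.4 = 65% of the benefit. With about 25 carriers per cluster, non-inferiority power is about 79%.
- No replacement: 15/55 = 27.3%, a fall of 15.6 points; 1 − 7.5/15.6 = 52% kept. With about 20 carriers per cluster, power is about 65%.

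The plan intends at least half of the benefit to be kept. No section of the SAP states this carry-over. ICC is held at 0.02 throughout.

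**The case against.** The strongest reply is that the sentence still names participants as its denominator, and that the exclusion comes straight after the non-VT category ("colonized with any other serotypes, excluding non-typable SP"). It can be read as fencing off that residual group: not VT, not non-typable, not negative. Redundant words are common in such definitions. The sections that govern the endpoint contain no exclusion, and 4.3.1 is descriptive. All of this stands. It shows that the carriers-only reading is not the only one and may not be the intended one. It does not remove the ambiguity, because the benign reading leaves half the clause without effect.

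Three further points stand:

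- The 25-35% band is not an automatic rule. The SAP says "The baseline prevalence of VT carriage is expected to be between 25 and 35" per cent, and makes re-estimation discretionary after steering-committee review; stratification is also that committee's decision. Protocol 7.12, however, plans a recalculation from baseline VT data, so the figure is used either way.
- The 70% comes from younger children in other countries before PCV introduction. At 85.7% or more the band is not breached at a true 30%.
- Treating non-typable isolates as non-VT is a definitional choice. The outcome is worded as non-VT serotypes, and leaving out isolates with no assigned serotype is compatible with that. A reader might infer that the SAP understates non-VT carriage; the documents do not define the category closely enough to say so. The defect is that the placement of these children is not stated.

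**Conclusion.** The concern holds as an ambiguity with consequences. SAP 4.3.1 contains an exclusion that is either redundant or changes the denominator. The second reading contradicts Protocol 6.1 and SAP 3.1.5, 3.2.1.1 and 4.3.2.1 without explanation. If applied that way at an assumed 70% overall carriage (60-80%), a true 30% would be reported as about 43% (38-50%). That could mislead the steering committee's two decisions, and would distort within-arm reductions and the seasonal analysis.

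A reader might infer three stronger conclusions that the documents do not support:

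- That the SAP has redefined the primary endpoint. The clause sits only under baseline characteristics, and its stated denominator is participants.
- That the trial would show a false vaccine effect. A baseline-only shift moves every arm and largely cancels in the between-arm contrast, provided overall carriage is balanced.
- That the non-inferiority margin or its power is undermined. The margin applies to the follow-up difference in the proportion of children with VT carriage, which has no exclusion. The figures in step 5 arise only if the baseline definition is carried over.

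**What to change.** Replace the sentence in SAP 4.3.1 and state that it applies to both surveys:

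- **Denominator:** all sampled children with a valid swab result, including culture-negative children and those with non-typable pneumococci.
- **VT carrier:** a child with at least one of the ten PCV10 serotypes.
- **Culture-negative:** a non-carrier of both VT and non-VT.
- **Non-typable:** not VT. State whether these isolates count as non-VT or are shown as a separate category; either way the children stay in the denominator.

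If baseline prevalence has already been tabulated for the steering committee, confirm which denominator was used.

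The cost is one SAP sentence. It needs no new data or field work, and no design figure changes: 30% to 15%, the 7.5-point margin and 94.4% power already rest on this denominator.

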4.3.2 Primary Analysis

4.3.2.1 Primary Analysis

The primary analysis is the test of the superiority of the full dose vaccination arm compared to the control arm, on the reduction in NP carriage. The reduction will be calculated by comparing the proportion of children carrying VT pneumococci 6 months post-vaccination to baseline, at the time of vaccination.

This primary analysis on the primary endpoint will be performed on the intent to treat population, using generalised estimating equations (GEE) to estimate risk differences and their associated 95% CI for the effect of the full dose vaccination on the reduction in VT carriage compared to the fractional dose. GEE will be used to account for clustering effect. Adjusted analyses with covariates (including but not limited to age, sex, vaccination coverage, time between baseline survey and vaccination, time between vaccination and follow-up survey, baseline prevalence of VT carriage) and stratification factor will be performed.

The administrative vaccination coverage for each site where vaccination campaign is performed, is obtained by the formula:

(number of vaccinees/number of expected children from the age group 1-9 years old) x 100.

The superiority will be tested at the 0.05 significance level.

For the non-inferiority analysis, the 95%CI around the risk difference in the proportion of children with VT carriage (full dose group – fractional dose group) will be using generalised estimating equations (GEE) and non-inferiority will be achieved if the lower limit of this 95%CI is >-7.5%.

Non inferiority analyses will be repeated on the per protocol population. Sensitivity analyses on the primary endpoint will be repeated by analyzing clusters according to the intervention they actually received if misallocation occurred.

In order to account for any potential seasonal variation seen due to timing of the surveys, additional sensitivity analyses will be performed, comparing the difference in prevalence between the full-dose and control arms, relatively to the reduction observed in the control group..

Multivariable logistic regression analyses will be performed to obtain adjusted estimates of risk factors for VT carriage at baseline and after vaccination campaign. The Odds Ratio and 95% CI will be adjusted for age and sex. Robust SE will be used to allow for clustering at the cluster level. 4.3.2.2 Secondary Analysis.

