11.5.3 Archiving

The Sponsor will securely store the final study database for at least 10 years. The Sponsor will also keep the Trial Master File and interim and final reports both in electronic and in hard copy form for at least 10 years.

12 Data Analysis

Analysis of all endpoints will be described in a Statistical Analysis Plan. This SAP will include all conventions on data, descriptive and statistical analyses to be performed on collected data during the conduct of the study. A brief overview is provided below.

Information on the total number of individuals per cluster for each of the following categories will be presented: screened individuals, screen failures (together with reasons for screen failure), consented participants for the baseline survey, the vaccination and the follow up survey.

Participant demographics and baseline characteristics will be described at the cluster level. For each arm of the trial the number of clusters, the average number of clusters by demographic and baseline characteristics, such as household composition, average prevalence of exposure to indoor smoke, etc will be described and compared to ensure comparability.

All analyses of outcome will be performed at the cluster level, controlling for clustering effects. For each cluster we will calculate the prevalence of NP carriage and present VT carriage in clusters allocated to full dose, fractional dose and control arm, including the 95% confidence interval.

Proportions will be compared using chi square or Fisher's exact test, as appropriate and adjusting for the clustering effect accounting for the intracluster correlation coefficient.

For the analysis of superiority of the full dose vaccination arm compared to the control arm, the comparisons will be done using a chi square test at the 0.05 significance level.

For the non- inferiority analysis, the 95%CI around the difference in the proportion of children with VT carriage (full dose group – fractional dose group) will be calculated and the non-inferiority will be achieved if the lower limit of this 95%CI is >-7.5%.

All sensitivity analyses and adjusted analyses will be described in the SAP. Sensitivity analyses will include, but not be limited to, analyses investigating potential seasonal differences in NP carriage of pneumococci.

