2.1 Primary Objective

The primary objective is to evaluate whether a mass vaccination campaign targeting children approximately 1-9 years of age with a full dose of PCV is superior to the absence of vaccine in reduction of VT carriage prevalence at 6 months post-campaign, and subsequently to evaluate if a single 20% dose of PCV is non-inferior to a full dose.

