4.1 Timing of Analysis

Determining whether mass campaigns with fractional dose PCV10 would accelerate herd protection against pneumococcal transmission in Sub-Saharan Africa

The primary endpoint will be the change from baseline in VT carriage at 6 months post-vaccination campaign. The reduction in VT carriage will be calculated by comparing the proportion of children carrying VT pneumococci 6 months post-vaccination to the baseline.

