4.3 Statistical Analysis

All results will be displayed by intervention group (full dose, fractional dose or control).

Descriptions of the study population will be provided at the individual level and at the cluster level as appropriate. Statistical analyses to demonstrate superiority and non-inferiority will be performed at the individual level. Non inferiority will be tested if the superiority of the full dose is shown; therefore, no adjustment for multiplicity is necessary.

Comparison between groups will be done at the cluster level using Student's t-test for continuous variables and Chi square test (or Fisher's exact test if more appropriate) for categorical variable.

Safety analysis will be done at the individual level only, and comparison for categorical variables will be done using a Chi square test (or Fisher's exact test if more appropriate). All comparisons will be done at the 0.05 significance level.

Prevalence of carriage will be presented with a 2 sided 95% confidence interval.

All statistical analysis will be performed on the statistical software Stata version 17 or later.

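### SAP 4.3.2.1 specifies the full-dose-versus-control superiority test with a GEE contrast against the fractional dose, and the plan does not settle whether that test is on 6-month prevalence or on change from baseline

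*Combined protocol and SAP*

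**What the plan says.** **Comparator.** SAP 4.3.2.1 opens: "The primary analysis is the test of the superiority of the full dose vaccination arm compared to the control arm". The next paragraph, still about this primary analysis, prescribes GEE in the intent-to-treat population to estimate risk differences "for the effect of the full dose vaccination on the reduction in VT carriage compared to the fractional dose". The non-inferiority comparison has its own GEE sentence further down the same section.

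Elsewhere the comparator is the unvaccinated arm. The primary objective (protocol section 6, SAP 2.1) asks whether a campaign "with a full dose of PCV is superior to the absence of vaccine in reduction of VT carriage prevalence at 6 months post-campaign". Protocol section 12 says that for "superiority of the full dose vaccination arm compared to the control arm, the comparisons will be done using a chi square test". The seasonal sensitivity analysis in SAP 4.3.2.1 is described as "comparing the difference in prevalence between the full-dose and control arms". SAP 3.1.2 sizes the superiority test against control.

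**Role of the test.** SAP 4.3: "Non inferiority will be tested if the superiority of the full dose is shown". The SAP gives this ordering as its reason for making no multiplicity adjustment.

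**Endpoint.** SAP 4.1: "The primary endpoint will be the change from baseline in VT carriage at 6 months post-vaccination campaign". Protocol 6.1 and SAP 4.3.2.1 also describe the reduction as 6 months compared with baseline. SAP 3.2.1.1, however, states: "The primary outcome is the prevalence of vaccine-type NP carriage in children approximately 1 to 9 years of age", assessed at both surveys. The non-inferiority rule is a difference in the proportion carrying vaccine types, with no baseline term. SAP 4.3.2.1 lists adjusted analyses, with baseline VT prevalence and the stratification factor among the covariates, but does not say whether the adjusted or the unadjusted estimate is primary.

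**The concern.** The superiority test is the gate to the non-inferiority test, which is the question the trial was mainly built to answer. An analyst who follows the SAP literally would produce a full-versus-fractional risk difference for the gate and would find no specified GEE estimate against control. Protocol section 12 does not fill the gap, because it names a chi-square test instead.

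The endpoint wording leaves a second choice open. The two surveys draw independent samples of children (protocol 7.5, SAP 3.1.1), so an unadjusted difference in change carries baseline sampling variance that the sample size does not include. If that is the primary estimate, the stated power above 90% for superiority has not been shown for it. If the choice is made after the 6-month data are seen, the pass or fail of the gate could depend on it.

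**Working it through.** **Inputs from the documents (protocol 7.12, SAP 3.1.2).** Baseline and control prevalence 30%; full dose at 6 months 15%; ICC 0.02; two-sided 5%; 27 full-dose and 9 control clusters; 36 households per cluster, one child each. The plan's own superiority calculation uses 9 clusters of 30 in each arm.

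**Assumptions not in the documents.** The between-survey cluster autocorrelation *c*, shown over its full range of 0 to 1, and no change in control-arm prevalence. A second cluster size, *m* = 30, is shown in case 36 is the number invited after a 20% increase (36/1.2 = 30); the plan can be read either way.

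**Formulas.** For *k* clusters of *m*:
- Single survey: Var = p(1−p)[1 + (m−1)0.02]/(km).
- Change between two independent surveys, with vb and vp the values of p(1−p) at baseline and at 6 months: Var = 0.02[vb + vp − 2c√(vb·vp)]/k + 0.98(vb + vp)/(km).
- Power = Φ(0.15/SE − 1.96), where SE² is the sum of the two arms' variances.

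**Step 1: reproduce the plan's own figure (9 × 30 per arm).** The design effect is 1 + 29 × 0.02 = 1.58.
- 6-month prevalence: 0.21 × 1.58/270 + 0.1275 × 1.58/270 = 0.001229 + 0.000746. SE 0.0444, power 92%. The stated 90% reproduces.
- Unadjusted change: power 62%, 71% and 81% for c = 0, 0.5 and 1. The stated 90% does not reproduce for any *c*.

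So the superiority size was calculated on 6-month prevalence. The non-inferiority size agrees with that reading: 27 × 36 per arm at 15% in both gives SE = √(2 × 0.1275 × 1.70/972) = 0.0211 and power Φ(0.075/0.0211 − 1.96) = 94%, against a stated figure of at least 90%.

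**Step 2: actual design, 6-month prevalence (27 versus 9 clusters).** At m = 36 the design effect is 1.70. The variances are 0.21 × 1.70/324 = 0.001102 (control) and 0.1275 × 1.70/972 = 0.000223 (full dose). SE 0.0364, power 98%. At m = 30, SE 0.0384, power 97%. The stated power above 90% holds.

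**Step 3: actual design, unadjusted difference in change.**

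| c | SE, m = 36 | Power, m = 36 | SE, m = 30 | Power, m = 30 |
|---|---|---|---|---|
| 0 | 0.0529 | 81% | 0.0558 | 77% |
| 0.5 | 0.0470 | 89% | 0.0503 | 85% |
| 1 | 0.0402 | 96% | 0.0440 | 93% |

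Power of 90% needs SE = 0.15/(1.960 + 1.282) = 0.0463, which corresponds to c of about 0.56 at m = 36 and about 0.83 at m = 30.

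**Step 4: effect of adjusting for baseline.** In a linear cluster-level model, regressing (6-month − baseline) on arm and baseline is the same as regressing 6-month prevalence on arm and baseline: only the baseline coefficient changes, by one. The arm effect is identical, so adjusted change does not pay the extra variance of Step 3. The SAP's model is an individual-level GEE, so this is a guide to what to expect there, not a proof.

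**The case against.** The comparator clause is very probably a drafting slip. The sentence refers back to an analysis just defined against control, every other statement of the objective names control or no vaccination, and full versus fractional has its own sentence. This stands as an account of what was meant. It does not make the clause right: no other SAP sentence specifies a GEE estimate against control. A reader might infer that the trial intends to gate on full versus fractional; the documents do not support that.

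On the endpoint, a reader might infer that the gate and the non-inferiority rule address different effects. They do not. Clusters are randomized after the baseline survey (protocol 7.11, SAP 3.1.3), so expected baseline prevalence is equal across arms, and the difference in change and the difference at 6 months target the same quantity with different precision. SAP 3.2.1.1 and 4.1 can even be read together, with prevalence measured at both surveys and then compared. In addition, the final statement of the non-inferiority rule gives no time point. That it means 6 months is a reasonable inference from the post-campaign wording in the sample-size sections and from SAP 4.1.1, but it remains an inference.

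The power loss also rests on an autocorrelation that the documents do not give. The low end requires cluster prevalence at the two surveys to be uncorrelated, and at 36 per cluster 90% is reached once *c* is about 0.56. Table 1 lists 36 per cluster under total participants, which weakens the 30-per-cluster case. Baseline prevalence is already a listed covariate, and power simulations for the Trial Steering Committee are already planned. All of this limits the endpoint point to a clarification. It does not answer which estimate is primary.

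**Conclusion.** The comparator clause in SAP 4.3.2.1 is wrong as written and must be corrected before the 6-month analysis, because it specifies the test that gates non-inferiority.

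The endpoint point is secondary. The plan words superiority on change from baseline but was sized on 6-month prevalence, and it does not name the primary estimate. If that estimate were an unadjusted difference in change, superiority power at 36 per cluster would be about 81% to 96%, against about 98% on 6-month prevalence, so the stated figure above 90% is not assured for it. The range assumes ICC 0.02, 30% versus 15%, an autocorrelation of 0 to 1, and neither stratification on nor adjustment for baseline prevalence.

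A reader might conclude that the trial is underpowered. The documents do not support that: the stated sample size is correct for 6-month prevalence, and adjustment for baseline prevalence is expected to remove most of the loss.

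**What to change.** 1. In SAP 4.3.2.1, change the comparator in the GEE sentence from the fractional dose to the control arm. Cost: one phrase.

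2. In SAP 3.2.1.1, 4.1 and 4.3.2.1 (and protocol 6.1 if needed), name one endpoint for superiority, state the time point of the non-inferiority measure, and say whether the adjusted or the unadjusted estimate is primary. The choice is the sponsor's. A cheap option, for both comparisons, is the GEE risk difference in 6-month VT carriage, adjusted for the stratification factor(s) and the cluster's baseline VT prevalence. It matches the sample size and still uses the baseline survey; the covariate is already collected and already listed. Cost: SAP wording and possibly a protocol clarification, with no extra data or participants.

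3. If unadjusted change is kept as primary, restate its superiority power, with the assumed autocorrelation made explicit, in the simulations already planned for the Trial Steering Committee (SAP 3.1.2).
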